Project title: A Comparison of the Post-Cesarean Section Analgesic Effects of Neuraxial Duramorph vs. Bilateral Transversus Abdominal Plane (TAP) Block With Combined Bupivacaine and Liposomal Bupivacaine (Exparel).

Clinicaltrials.gov name

A Comparison of the Post-C/S Analgesic Effects of Neuraxial Duramorph vs Bilateral TAP Block With Liposomal Bupivacaine

Submitted to IRB 4-5-2018

IRB# 2018-4-1-MMC

NCT: 03638011

Summary/Program Objective:

The primary objective is to reduce or eliminate the use of all narcotics/opiates for post Cesarean section pain management. We hypothesize that in comparison with epidural or intrathecal Duramorph, a TAP block with liposomal bupivacaine (Exparel) will provide better, longer-acting pain control and will significantly reduce the use of post-operative IV or p.o. opiates. This is a prospective, randomized clinical trial. We will compare the analgesic efficacy and duration of an ultrasound guided bilateral TAP Block (with combined bupivacaine and liposomal bupivacaine) to Duramorph (an opiate). Neuraxial duramorph provides approximately 24 hours of pain relief (analgesia), whereas a bilateral TAP block with liposomal bupivacaine is expected to provide up to 72 hours of analgesia. The patient's analgesia will be assessed by reviewing patient-reported pain intensity based on an 11-point numeric rating scale (NRS; 0= no pain, 10= worst possible pain) and post-operative opiate usage. Secondary objectives include a comparison of the opiate related post-surgical adverse events (AEs) (defined as somnolence, sedation, confusion, respiratory depression, dry mouth, nausea, vomiting, constipation, urinary retention and pruritus), and overall satisfaction with their postsurgical analgesia (patient-reported, using an 11 point scale whereby 0= not at all satisfied and 10= extremely satisfied) at hospital discharge.

Purpose of the study:

To determine if a bilateral transversus abdominal plane block with combined bupivacaine and liposomal bupivacaine can provide safe, effective, long-acting pain control that minimizes narcotic usage.

1. Specific Aims:

All patients will have neuraxial anesthesia (either a spinal or epidural) for their non-urgent or elective Cesarean section.

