The control group (Group 1) will receive either intrathecal or epidural Duramorph (preservative-free morphine sulfate). Post-operatively, participants will have orders to receive, on an as-needed basis, IV/oral acetaminophen and/or IV/oral non-steroidal anti-inflammatory drugs (NSAIDS) for mild-moderate pain, and narcotics for severe pain; specifically- oxycodone or hydromorphone. All patients must receive acetaminophen and NSAIDS (unless contraindicated) before receiving narcotics. This multi-modal pain management regimen is our current standard of care.

The experimental group (Group 2) will also receive a spinal or epidural anesthetic. This group will not receive neuraxial Duramorph for post-operative pain. Instead, the patient will receive an ultrasound guided bilateral TAP block with a combination of bupivacaine and liposomal bupivacaine solution immediately after the Cesarean section. Additionally, they will receive the same post-operative analgesia orders as group 1.

Specific Aim 1) To show that participants in the TAP block group will have better and longer acting pain relief than the Duramorph group. We will record and compare patient-reported post-operative pain intensity using an analogue visual score card with an 11-point numeric rating scale at 6, 24,48 and 72 hours.

Specific Aim 2) To show that the TAP block group will use less post-operative narcotics than the Duramorph group. We will measure and analyze the times at which participants in both groups request narcotics and the amount administered. We will also record each participant's pain level prior to receiving narcotics. It is anticipated that participants in TAP Block group will need significantly less post-operative narcotics when compared to the Duramorph group (standard of care)

Specific Aim 3) The TAP block group will have a decreased incidence of opiate- related side effects such as somnolence, sedation, confusion, respiratory depression, dry mouth, nausea, vomiting, constipation, urinary retention, and pruritus (itching).

Specific Aim 4) To measure patients' overall satisfaction with their postsurgical analgesia. Using an 11 point scale where 0= not at all satisfied and 10= extremely satisfied, we will record their overall satisfaction with their postsurgical analgesia. It is anticipated that participants in the TAP block group would report their pain control as being better than participants in the Duramorph group.

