This is a prospective, randomized study evaluating the effectiveness of abdominal analgesia when using 266 mg EXPAREL delivered into the bilateral TAP blocks. TAP blocks are an excellent method for providing adequate analgesia following lower abdominal surgery (3-6). To be eligible for the study, the patient has to be undergoing a non-urgent Cesarean section (either elective, or for non-urgent conditions such as failure to progress) with neuraxial anesthesia via an epidural, spinal or combination epidural/spinal. When patients arrive for their Cesarean section they will be assessed if they are eligible for the study and they will be asked to participate in the study after the risks and benefits are explained. If a patient does not want to participate, they will be offered TAP blocks with regular bupivacaine. Those patients who wish to participate will be asked to sign a study consent form. Patients that decide to participate in this study will be randomized to either group 1 or group 2 (like the

flip of a coin). Both groups will receive standard neuraxial anesthesia for their Cesarean Section and post-operative standard of care breakthrough medications for post-operative pain control. They will be randomized to receive either (group 1) standard neuraxial anesthesia with neuraxial Duramorph for post-operative pain or (group 2) standard neuraxial anesthesia without neuraxial Duramorph and a transversus abdominal plane (TAP) blocks immediately after surgery, with a mixture of bupivacaine and Exparel, for post-operative analgesia.

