There are only two groups in this study: Group 1 will have our present standard of care: neuraxial anesthesia, with Duramorph added to the epidural or spinal for post-operative pain. Group 2 will also have neuraxial anesthesia but will receive bilateral TAP blocks for post-operative pain control with 40 ml of 0.25% regular standard bupivacaine and with 20 ml of liposomal bupivacaine (Exparel) and 10-20 ml of normal saline (a salt solution, for a total of 70-80mls: 35-40 ml on each side). The TAP block plane will be identified with ultrasound. A 100 mm needle will be ultrasound guided into the TAP plane. 5-10 milliliters of normal saline will be used to hydro-dissect the plane. After hydro dissection 15 ml of 0.25% regular standard bupivacaine will be injected followed by 10 milliliters of liposomal bupivacaine (Exparel) diluted with 5 ml of 0.25% regular standard bupivacaine. This will be repeated on the opposite side. We will follow pain levels closely after the Cesarean section. If patients request medication for breakthrough pain, they will be given Tylenol, first. If the pain persists, they will be given Toradol 30 mgs, unless contraindicated. For persistent pain, they may receive another dose of 30 mgs of Toradol, but for severe pain they will be offered oxycodone 5-10 mg, depending on the intensity of the pain. Patients must be given both Tylenol and Toradol, unless contraindicated, before receiving narcotics for severe pain. We will ask you a set of questions to assess to quality of analgesia (pain control): 1) How is your pain at that time point? 2) What was your highest pain score? And 3) Did you require narcotic pain medication, when did you receive it and what was your pain level at that time? To assist your evaluation of your pain, we will show you a card that has a visual analogue (Faces) pains scale combined with numerical (0-10) analogue scale (0 is no pain, 10 is the worst pain you can imagine). We will be recording your pain at

- 6 hours after the end of anesthesia or the TAP block
- 24 hours after the end of anesthesia or the TAP block.
- 48 hours after the end of anesthesia or the TAP block.
- And at 72 hours after the end of anesthesia or the TAP block.
- Before you leave the hospital, we will ask you to rate your pain control.

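### No masking or sham is described for outcomes that are self-reported, nurse-reported or request-driven, and the study team, which expects the TAP block to win, asks the pain questions itself

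*Combined protocol and SAP*

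**What the plan says.** The Summary/Program Objective gives the design: "This is a prospective, randomized clinical trial". Neither there nor elsewhere in the available text is anyone described as masked, and the trial is not called open-label.

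The arms differ visibly in one respect. Section 1 (Specific Aims) says of both groups: "All patients will have neuraxial anesthesia (either a spinal or epidural) for their non-urgent or elective Cesarean section". In Section 3 (Research Design and Methods) the control treatment is "neuraxial anesthesia, with Duramorph added to the epidural or spinal for post-operative pain", so it goes through a route that both groups have anyway. In the experimental group, per Section 1, "the patient will receive an ultrasound guided bilateral TAP block with a combination of bupivacaine and liposomal bupivacaine solution immediately after the Cesarean section". No sham scan, sham block or matching dressing is described for the control group. On ward analgesia for the experimental group, Section 1 adds: "they will receive the same post-operative analgesia orders as group 1".

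On data collection, Section 3 says: "We will ask you a set of questions to assess to quality of analgesia (pain control". The woman is shown a combined faces and 0-10 card, and pain is recorded at 6, 24, 48 and 72 hours. The study team also asks her to rate her pain control before she leaves hospital. Side effects are asked of patients and/or the nurses caring for them. Narcotics are given on request after acetaminophen and an NSAID (unless contraindicated), and the oxycodone offered varies with pain intensity.

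Sections 1 and 2 record the team's expectation that the TAP group will have better pain relief, less narcotic use, fewer opiate side effects and higher satisfaction.

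**The concern.** Pain intensity (Aim 1) and satisfaction (Aim 4) are the woman's own ratings. Narcotic use (Aim 2) starts with her request and is scaled to the pain she reports. Side effects (Aim 3) come partly from her and partly from nurses, who are not described as masked either. If she or the person asking knows the group, expectation and the manner of asking can move these answers with no difference in analgesia.

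The team's recorded expectation runs the same way on all four aims. If it influenced the answers, the endpoints would tend to move together, so agreement among them would be weaker corroboration than it looks. A reporting shift also does not shrink as the trial grows, whereas the standard error does. A larger trial is therefore more likely to declare such a shift significant.

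**Working it through.** **Step 1: text check.** For each outcome, who supplies it, who collects it, and what masking is described:

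| Outcome | Supplied by | Collected by | Masking described |
|---|---|---|---|
| Pain 0-10 (Aim 1) | Woman | Study team, using a card shown to her | None |
| Narcotic times and amounts (Aim 2) | Woman's requests; dose offered depends on pain intensity | Recorded by the study team | None |
| Side effects (Aim 3) | Patients and/or nurses | Not specified | None |
| Satisfaction (Aim 4) | Woman | Study team, before discharge | None |

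**Step 2: illustration for the pain score.** The documents give no sample size, alpha, power or effect size, so there is no figure of the plan's own to reproduce. Inputs:

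- SD: 2.2 overall, and 1.4, 2.1, 1.9, 3.3 and 2.3 at 6, 12, 24, 48 and 72 h (Section 2, Table 1, 12 patients).
- Arm size n: assumed 50, with 30 and 100 as a range.
- Reporting shift b: assumed 0.5 point, with 0.25 and 1.0 as a range.
- True effect zero; two-sided 5% test (assumed); normal approximation.

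Formulas: SE = SD × √(2/n); d = b/SE; rejection rate = 1 − Φ(1.96 − d) + Φ(−1.96 − d).

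At n = 50, √(2/50) = 0.2, and with b = 0.5:

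- SD 1.4: SE = 0.28, d = 1.79, rate about 43%.
- SD 2.2: SE = 0.44, d = 1.14, rate about 21%.
- SD 3.3: SE = 0.66, d = 0.76, rate about 12%.

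At SD 2.2, varying the two assumptions:

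| Shift | n = 30 | n = 50 | n = 100 |
|---|---|---|---|
| 0.25 | 7% | 9% | 13% |
| 0.5 | 14% | 21% | 36% |
| 1.0 | 42% | 62% | 90% |

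Every entry would be 5% without a shift. The SDs come from patients who had both a TAP block and neuraxial morphine, a combination that neither trial arm receives, so they indicate scale only. The calculation covers the pain score and says nothing about opioid use, which the Summary names as the target of the primary objective.

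**The case against.** The strongest reply is that the documents are silent on masking, and silence is not proof. Consent pages are not part of the available text, and they are where one would expect to read what women are told about allocation. This stands. A reader might infer that the women know their group, but the documents never say so. The inference is strong, because one arm alone has a bilateral ultrasound-guided procedure and nothing is described that hides it, but it remains an inference.

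A reader might also infer that all answers are taken face to face, or by the people who performed the block. The card implies an in-person pain score. Nothing comparable is said for side effects or satisfaction, and nobody is identified as both blocker and questioner.

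The reply can add that not every outcome is equally exposed. Nurses can observe vomiting, respiratory depression and urinary retention. Narcotic times and amounts are recorded, and both groups have the same orders with non-opioids first. This narrows the concern without removing it: the nurses are not described as masked, and the narcotic pathway still begins with a request. Nor is the direction of bias established. The recorded expectation is the team's; the women's is unknown, and Duramorph is the standard of care.

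Finally, it is tempting to say that full concealment would be easy and cheap because both groups have neuraxial anesthesia. The documents do not support that. A woman who is awake may notice the scan and injections, and the protocol itself lists itching as an opiate effect, which could reveal the group.

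**Conclusion.** The concern holds in limited form. No masking, sham or masked assessor is described, the outcomes are largely self-reported or request-driven, and a team with a recorded expectation asks the pain questions. A favorable result on these outcomes would be hard to separate from expectation and interviewer effects.

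The size is unknown. Under the stated assumptions (no true effect, 50 per arm, 0.5-point shift), the false-positive rate for the pain score is about 21% at SD 2.2, and from about 43% down to 12% as the SD goes from 1.4 to 3.3. Shift and arm size are assumptions, and the effect on opioid use is not quantified. The documents do not support the stronger conclusion that women are known to be unmasked or that every endpoint is biased toward the TAP block. The trial can run without full masking, but the way answers are collected should change before enrollment.

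**What to change.** 1. Have the woman mark her own 0-10 score on the planned card at 6, 24, 48 and 72 h, and write her own satisfaction rating at discharge, instead of answering the study team aloud.
2. Where an existing team member who was not in the operating room is available, have that person hand out and collect the cards.
3. Do not volunteer the allocation to the woman until after the 72 h score, and say so in the consent form. Clinical staff keep full knowledge of what was given.
4. State in the protocol who is and is not masked, and acknowledge in the report that masking is partial. Matching dressings in both groups are optional and would conceal the group only in part.

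Cost: printed cards, a few minutes per patient and a line in the consent form. What remains: side-effect reports from nurses who know the group, and requests from women who have worked out their group. Self-marked cards reduce interviewer influence even where masking fails.

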The combination of these results suggest that the patients receiving TAP blocks with liposomal bupivacaine had significant postoperative pain relief (Table 1) and used little postoperative narcotic in comparison with neuraxial Duramorph.

Since our initial study of TAP blocks, (5), we have improved and refined our administration technique. We now consider liposomal bupivacaine to be like an infusion that should be initiated with a bolus (a large initial dose) in order to achieve therapeutic levels that will be maintained by liposomal bupivacaine. As per the Exparel liposomal bupivacaine package insert, bupivacaine HCl and EXPAREL may be administered simultaneously in the same syringe, and bupivacaine HCl may be injected immediately before EXPAREL as long as the ratio of the milligram dose of bupivacaine HCl solution to EXPAREL does not exceed 1:2' (7). Exparel® can be given with ½ the total dose of the bupivacaine found in the liposomes (266mg). That means we can co-administer 133 ml of 0.25% bupivacaine (=53.2 ml of 0.25% bupivacaine) with the liposomal bupivacaine. We will be adding 40 ml of the 0.25% bupivacaine, which is well below the maximal dose. From our experience and personal communications from other anesthesiologists, administering 30-35 ml on each side of the TAP block results in the 'best' block. We will explain our TAP block in the Methods section.

3. Research Design and Methods:

This is specifically for postpartum women. The purpose of this study is to test the effectiveness of Exparel (liposomal bupivacaine) administered in a bilateral TAP block to provide better analgesia after Cesarean section than neuraxial duramorph, which is the current standard of care: neuraxial Duramorph, and minimize use of post-operative narcotics and their annoying common side effects at one of the most enjoyable moments of life: having a new baby.

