At all-time points patients and/or nurses taking care of the patient will be asked about: somnolence (sedation or excessive tiredness), respiratory depression, hypoxia, dry mouth, nausea, vomiting, itching, constipation, urinary retention, sedation, and confusion.

We will also record time and date of any and all post-operative narcotics used by the patient as well as their pain scores just prior to receiving narcotics.

Additionally, patients will be asked about their overall satisfaction with postsurgical analgesia at the end of their hospital stay. If after Day 10±5, the investigator is made aware of an AE that occurred during this period of time, this will be reported to the IRB.

Eligibility Criteria:

Inclusion Criteria:

- Females, aged 18-45 years inclusive and ASA physical status 1-3.
- Undergoing non-urgent Cesarean section with neuraxial anesthesia/analgesia.
- Subjects must be physically and mentally able to participate in the study and complete all study assessments.
- Subjects must be able to give fully informed consent to participate in this study after demonstrating a good understanding of the risks and benefits of the proposed components of the TAP infiltration.

Exclusion Criteria:

- History of hypersensitivity or idiosyncratic reactions to amide-type local anesthetics
- Any subject whose anatomy, or surgical procedure, in the opinion of the Investigator, might preclude the potential successful performance of a bilateral TAP infiltration.
- Any subject who in the opinion of the Investigator, might be harmed or be a poor candidate for participation in the study.
- Any subject, who in the opinion of the Investigator, is on chronic pain medicine, including large doses of NSAIDs.
- Subjects who have received any investigational drug within 30 days prior to study drug administration, or planned administration of another investigational product or procedure during their participation in this study.

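### The stated purpose asks whether the TAP block is safe, but every planned adverse-event item is opiate-related or respiratory and none concerns the injection

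*Combined protocol and SAP*

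**What the plan says.** The combined protocol and SAP gives its purpose twice. Under Purpose of the study, the question is whether the block "can provide safe, effective, long-acting pain control that minimizes narcotic usage". At the start of section 3, Research Design and Methods, it reads "The purpose of this study is to test the effectiveness of Exparel (liposomal bupivacaine) administered in a bilateral TAP block to provide better analgesia" than neuraxial Duramorph, with less narcotic use and fewer narcotic side effects. Safety is not mentioned there.

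Two places describe an adverse-event comparison. The secondary objective in the Summary/Program Objective compares opiate-related events, "defined as somnolence, sedation, confusion, respiratory depression, dry mouth, nausea, vomiting, constipation, urinary retention and pruritus". Specific Aim 3 predicts the direction: "The TAP block group will have a decreased incidence of opiate- related side effects such as somnolence, sedation, confusion, respiratory depression" and the other listed effects.

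Data collection is described in section 3: "At all-time points patients and/or nurses taking care of the patient will be asked about: somnolence (sedation or excessive tiredness), respiratory depression, hypoxia". The other items on the list are dry mouth, nausea, vomiting, itching, constipation, urinary retention, sedation and confusion. The contacts are at 6, 24, 48 and 72 hours.

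One further sentence in section 3 concerns adverse events of any kind. It applies once Day 10±5 has passed and sets a condition and its consequence: "the investigator is made aware of an AE that occurred during this period of time, this will be reported to the IRB".

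Group 1 receives neuraxial Duramorph and no block. Group 2 receives no neuraxial Duramorph and has "transversus abdominal plane (TAP) blocks immediately after surgery, with a mixture of bupivacaine and Exparel, for post-operative analgesia".

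**The concern.** The two arms differ in two exposures: neuraxial morphine in Group 1 and a bilateral injection of local anaesthetic in Group 2. The question list covers the expected harms of the first in both arms and asks about no harm particular to the second. A problem caused by the injection would have no item to be recorded under, so its absence from the results would carry no information.

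What is at stake is how a favourable result is read. Fewer events in Group 2 would answer Aim 3. Set beside a purpose that includes the word safe, the same result could be taken as evidence on the safety of the block, a question on which the list collects nothing specific.

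**Working it through.** This is a comparison of text. The plan states no figure for this point, so there is none to reproduce.

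**Step 1. Match the items asked with the opiate-related definition.**

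| Opiate-related definition (Summary) | Item asked (section 3) |
|---|---|
| somnolence | somnolence, glossed to include sedation |
| sedation | sedation, listed again |
| confusion | confusion |
| respiratory depression | respiratory depression |
| dry mouth | dry mouth |
| nausea | nausea |
| vomiting | vomiting |
| constipation | constipation |
| urinary retention | urinary retention |
| pruritus | itching |
| (none) | hypoxia |

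The definition has 10 terms and the list asked has 11. All 10 terms are asked, and 11 − 10 = 1 item is additional: hypoxia, which is a respiratory item. Because somnolence is glossed as sedation and sedation appears again, the 11 items cover 11 − 1 = 10 distinct concepts, of which 9 come from the definition and 1 is hypoxia.

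**Step 2. Count items about the injection.** Items naming the injection site, the needle or a local-anaesthetic reaction: 0 of 11.

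**Step 3. Set the purpose against what can be compared.**

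| Element of the purpose | Planned comparison that addresses it |
|---|---|
| effective, long-acting pain control | pain scores at 6, 24, 48 and 72 hours (Aim 1) |
| less narcotic use | timing and amount of narcotics (Aim 2) |
| safe | opiate-related effects only (secondary objective, Aim 3) |

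**Step 4. Look for another source of safety data on the block.**

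- The Day 10±5 sentence covers any adverse event, but it depends on the investigator being told, goes to the IRB, and has no item list and no between-arm comparison.
- The exclusion of women with past reactions to amide local anaesthetics, and the requirement that participants understand the risks of the TAP infiltration, show that block risk was recognised. Neither is an outcome.
- The pilot series in Background reports pain, opiate use and satisfaction in 12 women and gives no adverse-event counts. Those women also received neuraxial morphine.

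None of these supplies outcome data on the injection.

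**Step 5. Check the timing of the contacts.** The block follows surgery directly, and the first contact is "6 hours after the end of anesthesia or the TAP block". Anything that happens and resolves before then would be known only from recall or nurse report, even if it were asked about. The wording also allows the clock to start at different moments in the two arms.

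**The case against.** The strongest reply is that the trial never undertakes to show safety. The word occurs once as a claim about the block, in the purpose line. It is absent from the primary and secondary objectives, the four aims and the restated purpose in section 3. This is correct, and it limits the point: one element of one statement of purpose lacks support, while the aims agree with the data collected.

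A second reply is that safe may mean sparing women the respiratory harms of opiates, which Background names as life-threatening and which the list does cover. The documents do not settle the meaning. Even so, that reading would concern opiate avoidance and would leave the block's own harms unexamined.

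A third is that the plan has safeguards: the exclusion criteria, and the check of the bupivacaine dose against the package-insert ratio. They show that risk was considered. They do not measure what happens.

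Some stronger readings are tempting, and the documents do not support them:

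- *The trial collects no other adverse events.* The Day 10±5 sentence refers to any adverse event and implies a period of observation. The text available for review ends at the exclusion criteria and omits the consent pages, so general collection described elsewhere cannot be ruled out.
- *The investigators plan to call the block safe on the strength of this list.* No sentence says so.
- *The block is hazardous, or its harms could never surface.* Nothing here shows a hazard. Some listed symptoms are non-specific and might arise from other causes. The documents list no symptoms of local-anaesthetic reaction, so the overlap cannot be counted from them. Apart from hypoxia, all of the items are defined in the plan as opiate-related.

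**Conclusion.** The point holds as a mismatch between one stated purpose and the planned data: 10 of 11 items are the opiate-related terms, one is hypoxia, and none is specific to the injection. A lower count in Group 2 would support fewer opiate-related side effects and no wider safety conclusion.

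It should be corrected, but it does not threaten the trial: the analyses of pain, narcotic use and satisfaction are untouched. The conclusion rests on the objectives, aims and question list as they stand in the text available for review. It assumes that no separate solicited list for the block exists elsewhere. It requires no assumption about sample size or event rates, neither of which that text gives.

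**What to change.** **Add items (preferred).** In section 3, at the 6, 24, 48 and 72 hour contacts already planned, add a short list of yes/no items, itemised by the investigators before enrolment:

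- suspected local-anaesthetic reaction, asked in both arms;
- injection-site problems, asked in Group 2 only.

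Report each descriptively by arm as number and percent with an exact 95% confidence interval. State four limits alongside:

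- no blinding is described, so answers may be influenced by knowledge of the arm;
- the time origin may differ between arms;
- events before 6 hours rely on recall or nurse report;
- zero events puts an upper bound on the risk and does not establish its absence.

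**If the items are not added.** Remove safe from the Purpose of the study so that it agrees with the purpose restated in section 3.

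**In either case.** State that the comparative conclusion from the existing list is limited to opioid-related side effects.

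**Cost.** A few more questions at contacts that already take place, with no new visit or call. The safety picture for the TAP arm may look less favourable once block problems are asked about, and the Group 2 items give no between-arm comparison. The wording option costs nothing in data collection but gives up the safety question.

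### Aim 3 side effects have no fixed informant, and somnolence overlaps sedation, so the recorded incidence can depend on who was asked and one event may be entered under two headings

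*Combined protocol and SAP*

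**What the plan says.** Side effects are a secondary outcome. The Summary/Program Objective states: "Secondary objectives include a comparison of the opiate related post-surgical adverse events (AEs", and gives ten terms: "defined as somnolence, sedation, confusion, respiratory depression, dry mouth, nausea, vomiting, constipation, urinary retention and pruritus". Specific Aim 3 carries the hypothesis over the same ten terms, introduced as examples: "The TAP block group will have a decreased incidence of opiate- related side effects such as somnolence, sedation, confusion, respiratory depression".

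Data collection is described in section 3, Research Design and Methods, just after the list of pain assessment times (6, 24, 48 and 72 hours). The sentence begins "At all-time points patients and/or nurses taking care of the patient will be asked about: somnolence (sedation or excessive tiredness" and its list ends with "itching, constipation, urinary retention, sedation, and confusion". Sedation thus appears twice in that sentence, once as part of the meaning of somnolence and once as its own item. The list also includes hypoxia, which neither the Summary nor Aim 3 contains.

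The text names no main informant, gives no rule for conflicting answers, does not require the source to be recorded, does not say what unit the incidence has, and describes no analysis for Aim 3. It describes no masking of patients or nurses.

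**The concern.** There are two separate weaknesses in one sentence.

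**Informant.** The wording permits the patient alone, the nurse alone, or both, and the choice may change between women and between visits. Nausea, itching, dry mouth and tiredness are felt by the patient, and a nurse asked in her place can miss them. Respiratory depression, hypoxia, urinary retention and confusion are better observed by staff. If the choice is left to the moment, the recorded rate partly measures who was asked. One group receives neuraxial morphine and the other a bilateral block after surgery, so staff may know the allocation, and the protocol states the expected direction. If the mix of informants differs by arm, the contrast shifts. If the source was never recorded, this cannot be repaired afterwards.

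**Overlap.** On the protocol's own explanation of somnolence, a sedated woman meets two of the listed terms. With no unit of incidence stated, nothing prevents one episode from being entered twice in a total.

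At stake is the claim that the block reduces opiate side effects, which is a named aim.

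**Working it through.** The plan gives no sample size, expected side-effect rate or test for Aim 3, so there is no figure to reproduce. **Every rate below is an assumption made for illustration.**

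**1. The lists side by side**

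| Place | Terms | Somnolence and sedation | Hypoxia |
|---|---|---|---|
| Summary/Program Objective | 10 | both listed | no |
| Specific Aim 3 | 10, as examples | both listed | no |
| Section 3, side-effect questions | 11 | both listed, one explained by the other | yes |

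**2. Effect of the informant on one rate**

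Let p be the true rate, and a and b the detection probabilities of patient and nurse, assumed independent with no false reports. The recorded rate is p·a (patient only), p·b (nurse only) or p·[1 − (1 − a)(1 − b)] (either).

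- p = 40%, a = 90%, b = 50%: 36%, 20%, and 40% × (1 − 0.1 × 0.5) = 38%.
- p = 40%, a = b = 70%: 28%, 28%, and 40% × (1 − 0.3 × 0.3) = 36.4%.

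Even two equally good informants give different rates depending on whether one or both are asked.

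**3. Effect on the comparison**

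Assume true itching of 50% (Group 1) and 20% (Group 2), full detection by the patient, half by the nurse, and a share w of women reported by the nurse alone. The recorded rate is p × (1 − 0.5w).

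- Same mix in both arms, w = 0.5: 50 × 0.75 = 37.5% and 20 × 0.75 = 15%. The difference falls from 30 to 22.5 points. The ratio stays at 2.5, since 50/20 = 37.5/15. An equal mix dilutes the difference.
- w = 0.25 in Group 1 and 0.5 in Group 2: 50 × 0.875 = 43.75% and 20 × 0.75 = 15%. The difference is 28.75 points and the ratio 2.92.
- The reverse: 50 × 0.75 = 37.5% and 20 × 0.875 = 17.5%. The difference is 20 points and the ratio 2.14.

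A modest imbalance in informants moves the ratio to either side of its true value of 2.5.

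**4. Effect of the overlap**

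Let s be sedation events and o other events per patient. If every sedation event is entered under both headings and headings are summed, the total goes from s + o to 2s + o, a rise of s/(s + o).

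- s = 0.2, o = 1.0: 1.2 becomes 1.4, +17%.
- s = 0.1, o = 1.5: 1.6 becomes 1.7, +6%.
- s = 0.3, o = 0.5: 0.8 becomes 1.1, +38%.

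For the proportion of women with any side effect, now let s be the proportion with sedation and q the proportion with some other effect, independent of it. The result is 1 − (1 − s)(1 − q). With s = 0.2 and q = 0.5 it is 1 − 0.8 × 0.5 = 60%, with or without the second heading. In a symptom-by-symptom table no total is inflated, but the two rows share cases.

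**The case against.** The strongest reply is that the wording may simply cover a mixed list, in which some symptoms need the patient and some the nurse, and that asking both improves detection. The patient is already questioned about pain at these contacts, and eligibility requires that she can complete the assessments, so wholesale reporting by nurses is unlikely. This stands as a limit on size. It does not supply the missing rule, because the text does not say that both are always asked or which answer prevails.

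Three stronger readings are tempting and are not supported.

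- *That a sedation episode is counted twice.* The documents define no sum or score. Double counting arises only if events or headings are added up.
- *That one arm is reported by nurses and the other by patients.* With the itching figures above this would give a difference of 40 points (50% v 10%) or 5 points (25% v 20%), but nothing in the protocol suggests such a split.
- *That sleepy or vomiting women are the ones a nurse answers for.* This is plausible, but no passage says so.

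It is also fair to say that making the patient the informant does not remove the masking problem, since she may know whether she had a block. And relying on the patient alone for sedation would lose the most sedated women. Both points stand, and the second shapes the fix.

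**Conclusion.** The concern holds as an ambiguity in a secondary outcome that is cheap to remove before enrolment and hard to remove afterwards. The recorded Aim 3 incidence can depend on the informant. The comparison is diluted on the difference scale if the mix is equal between arms, and could be biased in either direction if it is not. The documents do not show that the mix will differ. Somnolence and sedation overlap as listed, and the consequence depends on a unit of incidence that the plan does not state: inflation of a summed count, overlapping rows in a symptom table, and no effect on a per-patient any-symptom proportion.

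No size can be derived from the documents. The illustrations rest on assumed rates and detection probabilities, no false reports, independent informants and a single report per woman, whereas the plan asks at repeated time points. They show sensitivity and are not forecasts. The primary objective is not touched.

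**What to change.** In section 3, replace the open choice of informant with a fixed source for each symptom, the same at every time point and in both arms:

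- **Patient, fixed yes/no list:** nausea, itching, dry mouth, constipation.
- **Nurse or chart, for every patient:** respiratory depression, hypoxia, vomiting, urinary retention, confusion.
- **Both, for every patient:** one merged somnolence/sedation item, counted as present if either reports it, with the source recorded.

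Make the lists in the Summary/Program Objective and Specific Aim 3 match, and state whether hypoxia counts as an opiate-related effect. Define the Aim 3 incidence as the proportion of patients with each symptom and the proportion with any symptom.

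The cost is revised wording and a one-page checklist used at contacts already planned. Some patient-reported items will be missing when a woman cannot answer. Patient reports remain unmasked, and so may nurse reports; the change makes ascertainment uniform but does not blind it.
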